Official title: EVALUATION OF A RESPIRATORY MUSCLE TRAINING PROGRAM RESTRICTING NASAL BREATHING WITH FEELBREATHE® DEVICE IN COPD PATIENTS

Date of the document: 04-04th-2017

Background

The benefits of pulmonary rehabilitation programs (RP) in chronic obstructive pulmonary disease (COPD) patients have been shown and are recognized as an effective tool for improving dyspnea, exercise tolerance and quality of life in all the guidelines(1)(2)(3).

Inspiratory muscles training (IMT) has been used as a complement added to the supervised pulmonary RP and some studies have shown an improvement in the inspiratory muscles strength, tolerance to exercise (Oxygen uptake efficiency slope), dyspnea and distance walked in the six minutes walking test (6MWT) after a inspiratory muscles training program in patients with COPD (4).

The Feelbreathe® device, tested in our study can be used in static and dynamic situations (5) and is a nasal ventilatory flow restriction device made by a strip of hypoallergenic material (3M Spain, S.A. Medical Specialties / O.E.M.) that is placed and adhered under the nostrils impairing the free pass of air through the nose by producing resistance to flow. The Feelbreathe® device (FB) has been authorized by the Spanish Agency for Medicines and Health Products for application on COPD patients (Expedient 521/15/EC. AEMPS-Madrid-Spain-Patent N°: P200902402).

Previous studies have shown that an increased airflow resistance while breathing nasally, during exercise, increases the breathing effort (6) which may potentially improve the exercise tolerance (7) and energy efficiency (8). In healthy subjects FB has shown changes in lung ventilation, gas exchange and heart rate during exercise with improvements on ventilatory efficiency (9).

So, the objective of this study was to assess the effects of a nasal restriction device for inspiratory muscle training adding to a rehabilitation program on exercise capacity (Oxygen uptake efficiency slope), quality of life, dyspnea and inspiratory muscle strength in stable COPD patients.

STUDY PROTOCOL AND STATISTICAL ANALYSIS PLAN

Participants

Subjects were recruited from the Pneumology outpatient of the University Hospital Puerta del Mar in Cádiz (Spain). Consecutive patients were screened by reviewing their charts and by interview. Inclusion criteria were diagnosis of COPD according to guidelines criteria (1) (10) with moderate or severe airflow obstruction (GOLD 2 or 3)(10), dyspnea grade 2 or greater by mMRC scale and a stable clinical condition for at least 2 months. Exclusion criteria were poor compliance, treatment with oxygen therapy or non-invasive mechanical ventilation, CO₂ retention, medical conditions that can produce or increase dyspnea on exercise in addition to COPD (cardiovascular, metabolic or other respiratory diseases) or osteoarticular or neuromuscular diseases that may limit the correct performance of the 6MWT. A total of 36 patients were included in this study.

Written informed consent was obtained from all patients before starting the study. This clinical trial received ethical approval from the Ethics Committee University Hospital Puerta del Mar and met the requirements of the Declaration of Helsinki.

Design

Participants were randomly assigned according to a computer-generated randomization table to three groups: 1) those who participated in the supervised RP using the Feelbreathe® device (FB group), 2) those who participated in the supervised RP with oronasal breathing without Feelbreathe® device (ONB group) and, 3) those included in the control group (CG) which received standard medical recommendation for patients with COPD.

Demographic and clinical data were recorded. Dyspnea was assessed by the modified Medical Research Council (mMRC) dyspnea questionnaire (11) and quality of life by the COPD Assessment Test (CAT) questionnaire (12). Spirometry was performed according to American Thoracic Society criteria (13)(14) {Formatting Citation} (Spirometer CPX, Cardinal Health, Hoechberg, Germany). Then, they performed a resting electrocardiogram (QRS Universal ECG, QRS, Plymouth, MN, USA). P_{lmax} was measured during a maximal, static inspiratory effort measured at the mouth (Micro RPM, Micro Medical Ltd., Chatham, Kent, UK). P_{lmax} was recorded as the highest value averaged over 1s from three maneuvers that varied by less than 10% and was measured based on three maximal reproducible respiratory efforts. Then, an incremental test on treadmill (Technogym Run Race 1400HC, Gambettola, Italy) was performed to determine the VO_2 peak (Circuit Spirometry Vmax 29C, Sensormedics, USA). While performing the tests, the cardiac response was measured every 10s (JECG 12 Canal, Friedberg, Alemania). Blood oxygen saturation percentage (Ear oximeter, Hewlett-Packard 47201A, Corvallis, EEUU) and respiratory gas exchange were measured every 5 sand breath by breath respectively, throughout the test. Finally, one week apart, the patients performed the 6MWT according to the ATS guideline (15).

All tests were performed according to a standardized protocol before starting the training and 2 days after its completion.

Training program

Participants carried out a supervised RP for 8 weeks, 3 days per week. The training sessions lasted 60 minutes and included a warming up phase, a main phase and a recovery phase. After each session, Borg's perceived exertion was measured. The RP included aerobic exercise on cycle ergometer and on treadmill (progressing since 10' to 30' and since 40 to 75% of the reserve heart rate (RHR) or 6-7 score based on Borg's perceived exertion), strengthening of lower and upper limb muscles groups, breathing exercises (pursed lip breathing, diaphragmatic and abdominal breathing and diaphragmatic mobility) and finally stretching exercises.

In the FB group, for restricted nasal breathing, at the beginning of the training program, the small size device was used (4 mm). The size of the device was progressively increasing according to the patient adaptation to the 5 or 6 mm device,

depending on the score on Borg's perceived exertion scale. If the patient has a score under 4 after the RP sessions the size of the FB device was increased.

FB was placed under the nostrils, using sterile gloves and assessing the patient did not have mucus or injuries. The device was used during the RP and patients were invited to have a physiological breathing by nasal inspirations and mouth expirations.

Statistical Analysis

Descriptive data of the participants are expressed as mean \pm standard deviation or number and percentage for continuous and categorical variables respectively. Percentage of change (%_{Change}) for each variable was calculated as:

$$\%_{\text{Change}} = (\text{mean(Post-test value)} - \text{mean(Pre-test value)}) / \text{mean(Pre-test value)} * 100$$

Differences among RP (between differences) and between pre- and post RP tests within each breathing condition (within differences) were analysed using a Bayesian hierarchical model. 6MWT distance, P_{lmax} and CAT were considered as continuous variables while mMRC dyspnea was treated as an ordinal variable. To analyse differences at baseline only a categorical variable indicating the RP (GC, ONB or FB) was introduced in the model as predictor. However, to analyse both between and within differences RP, time (pre- or post-PR) and their interaction were introduced as predictor variables. Due to the sample size in our study we choose to analyse our data using Bayesian inference since it has proven to be a proper method of statistical inference for small sample size (16)(17). Inference was performed based on the 95% credible interval (95% CrI) which contains a range of values where we can be 95% certain that the true value lie given the data at hand and the model fitted. The Bayesian hierarchical model was fitted using the package *brms* for the R programming language for statistical computing and graphics (18). All parameters estimated showed a good convergence with values of $\hat{R} = 1$ and number of effective sample size > 1000 . Further analysis can be found in the supplemental file while the code and the dataset to replicate it are stored in https://github.com/[name]/COPD_2_1.

References

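### Entry requires mMRC grade 2 or more and mMRC is then tested pre to post within each arm; unless the analysed pre-value is a separate, uncut reading, within-arm dyspnoea change is expected to drift towards improvement with no true change

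*Combined protocol and SAP*

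**What the plan says.** Four statements matter, all in the combined protocol and SAP.

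- **Entry (Participants).** Patients need "dyspnea grade 2 or greater by mMRC scale and a stable clinical condition for at least 2 months". On how they were found: "Consecutive patients were screened by reviewing their charts and by interview". The total is stated as "A total of 36 patients were included in this study".
- **Allocation (Design).** "Participants were randomly assigned according to a computer-generated randomization table to three groups": rehabilitation programme (RP) with the device (FB), RP without it (ONB), and control.
- **Measurement (Design).** "Dyspnea was assessed by the modified Medical Research Council (mMRC) dyspnea questionnaire". This stands after the randomisation text and apart from the screening text. Tests were done "before starting the training and 2 days after its completion", and the programme ran for 8 weeks (Training program).
- **Analysis (Statistical Analysis).** Differences among arms and differences "between pre- and post RP tests within each breathing condition (within differences) were analysed using a Bayesian hierarchical model". mMRC is ordinal; RP, time and their interaction are the predictors; inference rests on the 95% credible interval. A percentage change from pre and post means is also computed for each variable.

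The document does not say whether the grade that qualified a patient is the pre-training grade in the analysis, or whether the grade 2 rule was checked again at baseline. It does not mention regression to the mean, and it does not rank the between-arm comparison above the within-arm changes.

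**The concern.** mMRC is a five-grade self-report scale, and a single reading carries error. A rule that admits only grades 2 to 4 takes in some patients whose reading happened to be high that day and leaves out some whose reading happened to be low. If that same reading is the pre-value, the next one falls on average even when nobody has changed, because the post-training grade is free to be 0 or 1 and the pre-training grade is not. A model with RP, time and their interaction has no term for this, so the drift goes into the time effect within each arm.

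Dyspnoea is part of the stated objective and within-arm change is a named analysis. At stake is a statement such as 'dyspnoea improved in the FB arm', drawn from a within-arm credible interval or percentage change that may partly reflect selection.

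**Working it through.** **No figure to reproduce.** The document gives no sample-size calculation, error rate, mMRC reliability or grade distribution. The check therefore asks how large the drift could be under stated assumptions.

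**Inputs from the document.** Entry at mMRC 2 or more; one pre and one post reading; 36 patients in three arms. The allocation ratio is not stated; equal arms would give 36 / 3 = 12.

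**Assumptions.** A latent normal dyspnoea score cut into grades 0 to 4; test-retest correlation r from 0.60 to 0.95; no true change; four source-population mixes (percent in grades 0/1/2/3/4). Paired and two-sample t intervals stand in for the Bayesian ordinal model.

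**Case (a): the qualifying grade is the pre-value.** With S the qualifying grade and F the post grade,

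expected change = E[F | S ≥ 2] − E[S | S ≥ 2], where E[F | S ≥ 2] = Σ P(F ≥ k | S ≥ 2) for k = 1 to 4.

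Worked example, mix 15/30/28/19/8, r = 0.80:

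- Pre mean = (2×0.28 + 3×0.19 + 4×0.08) / (0.28 + 0.19 + 0.08) = 1.45 / 0.55 = 2.64.
- Post mean, from the bivariate normal = 0.987 + 0.815 + 0.463 + 0.144 = 2.41.
- Expected change = 2.41 − 2.64 = −0.23 grade. By simulation, 36% of patients 'improve' and 18% 'worsen'.

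Mean change, with the one-arm false-improvement rate at n = 12 in brackets (nominal 2.5%):

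| Source mix | r = 0.60 | r = 0.80 | r = 0.90 | r = 0.95 |
|---|---|---|---|---|
| 15/30/28/19/8 | −0.40 (21%) | −0.23 (12%) | −0.14 (9%) | −0.09 (7%) |
| 10/35/30/18/7 | −0.37 (21%) | −0.21 (12%) | −0.14 (10%) | −0.09 (7%) |
| 5/20/35/28/12 | −0.21 (10%) | −0.12 (7%) | −0.08 (6%) | −0.05 (4%) |
| 2/10/33/35/20 | −0.11 (5%) | −0.06 (4%) | −0.04 (4%) | −0.03 (2%) |

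The chance that at least one of three arms falsely shows improvement is 1 − (1 − p)³. For p = 0.21 it is 1 − 0.79³ = 0.51; for p = 0.09 it is 1 − 0.91³ = 0.25; at the nominal 0.025 it is 1 − 0.975³ = 0.07.

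**Case (b): separate baseline reading, grade 2 cut applied again.** Mean change is −0.29 to −0.02 grade over the same grid.

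**Case (c): separate baseline reading, no second cut, independent error.** Mean change is 0.00, and the false-improvement rate does not exceed nominal.

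**Between-arm contrast under (a).** The difference in change between two randomised arms averages 0.00, and its two-sided false-positive rate is about 5% throughout. All arms pass the same entry rule, so the drift cancels in expectation.

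**The case against.** The strongest objection is that the text leans towards case (c). Screening by chart and interview is described in one place, and the mMRC questionnaire in another, within the pre- and post-training assessments. Two described steps suggest two readings, and with independent errors and no second cut there is no drift. This stands as far as it goes: the document suggests a separate reading but does not state one, and it says nothing about a second check of the cut.

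A reader might infer three stronger things, none of which the document supports:

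- *That regression to the mean produces an improvement in every arm.* The shift is one of expectation and depends on the unstated premise. Even under case (a), an observed fall in all three arms occurred in only about 10% to 66% of simulated trials in the last three mixes of the table.
- *That the bias is necessarily large.* The larger figures need a source population with about 45% in grades 0 and 1. In the most breathless mix at r = 0.95 the shift is −0.03 grade and the error rate is about nominal. The entry requirement of two months' stability may also reduce selection on a passing worsening, though it does not remove reporting error in a single grade.
- *That the device comparison is compromised.* The effect of adding the device is a between-arm question. The model contains that contrast, with a concurrent randomised control.

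The point is made for mMRC because mMRC is the outcome on which entry was cut. Whether CAT could drift too, by sharing transient variation with mMRC, cannot be judged from the document.

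**Conclusion.** The concern holds in conditional form. The plan selects on mMRC and then draws within-arm inference on mMRC, without saying whether the analysed pre-value is free of the entry cut. If it is not, the expected within-arm change is biased towards improvement in all three arms: about −0.40 to −0.03 grade if the qualifying grade is reused, with a false improvement in one arm in about 2% to 21% of trials against a nominal 2.5%. If the baseline is a separate, uncut reading with independent error, the bias is 0.00.

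The ranges rest on assumed case mixes, assumed correlations of 0.60 to 0.95, 12 patients per arm, and t intervals in place of the ordinal model. The direction does not depend on the choice of mix or correlation; the size does. The exposure is confined to reading within-arm mMRC change and mMRC percentage change as evidence of benefit. It does not bias the randomised comparison under no effect.

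**What to change.** In the Statistical Analysis section:

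1. State that all dyspnoea conclusions rest on the between-arm RP-by-time contrast already in the model.
2. Label within-arm mMRC change and mMRC percentage change as descriptive, with no claim of improvement drawn from their credible intervals.
3. Say whether the analysed pre-training mMRC is a reading separate from the screening grade, and whether the grade 2 cut was applied to it again. Keep within-arm inference for mMRC only if it is separate and the cut was not re-applied.

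This needs no new data and no new model. That matters because the section already reports convergence of fitted parameters, so a further baseline reading could not be added for these 36 patients. The one small cost is that the within-arm dyspnoea claims are lost unless the condition in item 3 is met.

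### The only post-test is timed from completion of training, and no as-randomised analysis is stated, so the arm contrasts could become completer comparisons that favour the device

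*Combined protocol and SAP*

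**What the plan says.** The combined protocol and SAP sets the assessment times in one sentence at the end of the Design section: "All tests were performed according to a standardized protocol before starting the training and 2 days after its completion". The Training program section says what is to be completed: "Participants carried out a supervised RP for 8 weeks, 3 days per week", that is 8 × 3 = 24 sessions. It gives no minimum attendance. The third arm consists of "those included in the control group (CG) which received standard medical recommendation for patients with COPD", so it has no training to complete.

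Eligibility is described under Participants: "Consecutive patients were screened by reviewing their charts and by interview". The list of exclusions opens with "Exclusion criteria were poor compliance" and continues with respiratory support, CO₂ retention and other medical conditions. The section ends its account of recruitment with "A total of 36 patients were included in this study", without saying whether these are the patients randomised or the patients analysed. Design then states "Participants were randomly assigned according to a computer-generated randomization table to three groups"; the allocation ratio is not given.

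The Statistical Analysis section describes a Bayesian hierarchical model with group, time and their interaction. It names no analysis population and no rule for missing post-tests. Nowhere does the document plan to report attendance, device use, withdrawals or tolerability by arm.

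**The concern.** The assessment sentence decides when patients are tested and, on its plain wording, also who is tested. A patient who leaves in week 3 never completes training, so nothing triggers a post-test. Nothing in the analysis section offsets this by committing to all randomised patients.

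Both training arms share this trigger, but they do not share every reason for stopping. FB patients train with a strip that adds resistance to nasal airflow, and all patients enter with dyspnea of mMRC grade 2 or more. Intolerance of the strip is therefore a possible cause of loss in the FB arm only. If it operates, FB-ONB sets patients who tolerated rehabilitation plus restriction against patients who had only to tolerate rehabilitation. The contrasts with control are also exposed, because control patients cannot stop training. Selection of this kind acts after randomisation, and no planned outcome would show it.

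**Working it through.** **No figure to reproduce.** The document states no dropout rate, effect size, SD or power. The 36 is a count. Everything below is illustration. It assumes 12 per arm (36 / 3) because the split is not stated.

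**1. What each arm's post-test depends on, read literally**

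| Arm | Training to complete | Post-test defined for | Causes of early stopping |
|---|---|---|---|
| FB | 24 sessions with the strip | completers | rehabilitation, or the strip |
| ONB | 24 sessions | completers | rehabilitation |
| Control | none | nobody (no date given) | not applicable |

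**2. Completers against all randomised patients.** Assume a 6MWT gain of 40 m in every completer of either training arm, 0 m in stoppers, one ONB stopper and k FB stoppers.

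- Completers: 40 - 40 = 0 m for FB-ONB, whatever k is.
- All randomised: FB mean = (12 - k)/12 × 40; ONB mean = 11/12 × 40 = 36.7 m.

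| k | FB mean (m) | FB-ONB, all randomised (m) |
|---|---|---|
| 0 | 40.0 | +3.3 |
| 1 | 36.7 | 0 |
| 2 | 33.3 | -3.3 |
| 3 | 30.0 | -6.7 |
| 4 | 26.7 | -10.0 |

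Each further FB stopper shifts the gap by 40/12 = 3.3 m. For k = 0 the completer comparison works against the device, and for k = 1 it does no harm. It favours FB only when FB loses more patients than ONB. Against control, the completer mean overstates the as-randomised FB mean by k/12 × 40 m: 6.7, 10.0 and 13.3 m for k = 2, 3 and 4.

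**3. A second model with selection on outcome.** Assume no true effect, no loss in the comparison arm, and loss of the least tolerant FB patients. With p the share of FB missing and rho the correlation between tolerating the device and the outcome, the apparent FB benefit in SD units is rho × φ(z_p)/(1 - p), where φ is the standard normal density and z_p its p-quantile.

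| FB missing | rho 0.3 | rho 0.5 | rho 1 |
|---|---|---|---|
| 0 of 12 | 0 | 0 | 0 |
| 1 of 12 | 0.05 | 0.08 | 0.17 |
| 2 of 12 | 0.09 | 0.15 | 0.30 |
| 3 of 12 | 0.13 | 0.21 | 0.42 |
| 4 of 12 | 0.16 | 0.27 | 0.55 |

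For scale, the approximate 95% half-width of a two-arm difference is 1.96 × √(1/12 + 1/(12 - d)), with d missing. It is 0.80 SD for d = 0 and 0.90 SD for d = 4.

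**4. How easily such losses arise.** If each patient independently drops out with probability 10%, 20% or 30%, the chance of losing 3 or more of 12 is 11%, 44% or 75%. These rates are assumptions.

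**5. What the planned analysis does with missing post-tests.** A hierarchical model can keep a patient with only a pre-test, but the plan does not say that it does. Even then, the estimate relies on the missing value being predictable from what was observed, which is doubtful when patients leave through intolerance. The percentage-change formula divides by a group pre-test mean and uses a separate group post-test mean. If post-tests are missing, the two means could come from different patients.

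**The case against.** The assessment sentence can be read as setting a time and not a condition: completion may mean the end of the 8-week programme, in which case an early stopper could still be tested. No attendance threshold appears, and no rule denies anyone a post-test. FB and ONB share the programme and the sentence, so their contrast is biased only if dropout or its reasons differ. The FB arm began with the smallest device and moved up with adaptation and exertion score, which bears on tolerance. The document reports no dropout, and the supplemental file and repository that it mentions, not available here, may give the numbers analysed. At modest correlation (0.3) the bias in step 3 is small beside the interval width. All of this stands. It makes the size uncertain, but it does not supply the missing commitment to test and analyse everyone randomised.

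A reader might also infer more than the text supports:

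- **That poor compliance was used to remove patients after randomisation.** It is listed with conditions that are established before entry, next to screening by chart and interview, and before randomisation is described. Applied then, it affects all three arms alike: it limits generalisability and does not bias the comparison.
- **That every control patient was post-tested.** The same literal reading leaves controls with no test date at all.
- **That the plan does hide an intolerable device.** The documents show only that it could.

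**Conclusion.** The point holds as a gap in who is post-tested and analysed. On its plain wording the only post-test belongs to patients who complete training, and no as-randomised population is stated. The FB arm has one more possible reason for loss than the ONB arm, so FB-ONB and the contrasts with control could become completer comparisons that favour the device.

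The size cannot be fixed from the documents. With nobody missing it is zero. With 2 to 4 of an assumed 12 FB patients missing, it is 3.3 to 10 m on FB-ONB under the assumptions of step 2, or 0.09 to 0.55 SD under those of step 3. The direction rests on FB losing more patients than ONB, and on those who stop for intolerance doing less well than those who stay.

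**What to change.** - **Design (assessments):** hold the post-test 2 days after the end of the 8-week period, counted from the same starting point in all three arms, for every randomised patient, whatever the number of sessions attended or the use of the device.
- **Statistical Analysis:** base the FB-ONB and control contrasts on all randomised patients in their assigned arm, keep those with only a pre-test in the hierarchical model, and present completers as a secondary analysis.
- **Participants (clarification):** state that poor compliance is judged only before randomisation.
- **If the data are already collected,** as the reported model convergence suggests: apply the as-randomised analysis and report by arm the numbers randomised, stopped and post-tested.

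The cost is some rewording and, if still possible, a few visits that were already planned for these patients. The estimated FB effect may come out smaller.

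### Does the Borg 6-7 training target block the device step-up rule that needs a Borg score under 4?

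*Combined protocol and SAP*

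**What the plan says.** All the rules are in the Training program section of the combined protocol and SAP.

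- **Aerobic intensity (both trained arms).** Cycle and treadmill work progresses over "40 to 75% of the reserve heart rate (RHR) or 6-7 score based on" the Borg rating. The link between the two criteria is *or*, and no sentence says which one governs.
- **Session and rating.** "The training sessions lasted 60 minutes and included a warming up phase, a main phase and a recovery phase". On timing, the section says: "After each session, Borg's perceived exertion was measured".
- **Device (FB arm only).** Training starts on the 4 mm device. "The size of the device was progressively increasing according to the patient adaptation to the 5 or 6 mm device", with the Borg score as the guide. The trigger is: "If the patient has a score under 4 after the RP sessions the size of the FB device was increased".

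The Background section cites earlier work in which nasal airflow resistance during exercise "increases the breathing effort". The Design section sets supervised rehabilitation with the device against the same supervised rehabilitation without it (ONB), plus a control group. The Statistical Analysis section models group, time and their interaction, with no term for training load.

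**The concern.** The aerobic target is a Borg score of 6 or 7 and the device is enlarged when the score is under 4. Only one Borg measurement is described. If it serves both rules, a patient who trains as intended can never earn a larger device, and a patient who earns one is not training as intended. Device progression would then depend on whether staff steered by heart rate or by exertion, not on adaptation to the device.

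A second worry follows from the Background. If the device makes breathing harder and exercise is steered by perceived effort, FB patients might reach the same rating at a different work rate from ONB patients.

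Both points touch FB versus ONB, the contrast that isolates the device. A stalled inspiratory load would dilute any effect on PImax. Unequal aerobic load would mix a training difference into a device effect. With 36 patients in three groups there is little room for either.

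**Working it through.** The plan states no figure on this point, so there is none to reproduce. The check compares the two rules and asks when they refer to the same score.

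**Inputs (Training program section).** Target 6-7; step-up under 4; 8 weeks at 3 sessions a week; device sizes 4, 5 and 6 mm.

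**1. Overlap.** The lowest target score is 6 and the step-up limit is 4: 6 − 4 = 2. A qualifying score therefore lies more than 2 points below the target. The ranges are disjoint.

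**2. The worst case.** Sessions = 8 x 3 = 24. If every post-session score were 6 or 7, the rule would be met in 0 of 24 and the device would stay at 4 mm. This restates the premise. It needs a constant target from the first session, Borg rather than heart-rate steering, and one score serving both rules.

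**3. Whether the text supports those premises.**

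| Premise | What the section says |
|---|---|
| Constant target from the start | Duration and intensity progress; 6-7 can be an end point |
| Borg governs | It is an alternative to heart rate, which starts at 40% of reserve |
| Same score for both rules | 6-7 is attached to the cycle and treadmill work; the step-up score follows the whole session |

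The whole session also contains strengthening, breathing exercises, stretching and a recovery phase. A rating taken at its end need not equal the rating during aerobic work, and it cannot have steered the exercise already done. None of the three premises is stated.

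**4. How often the rule must fire.** From 4 to 6 mm through 5 mm is two steps. If one qualifying score moves one size (an assumption, since the number needed is not stated), the rule must be met in 2 of 24 sessions to reach the largest device. Low scores early in the progression, or after recovery, could supply them.

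**5. The scale (not named).** On an assumed 0-10 scale both values are usable. On an assumed 6-20 scale a score under 4 cannot occur, but 6-7 would then be the bottom of the scale, which makes no sense as a training target. The two values together point to 0-10.

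**6. Load in FB and ONB.** Equal ratings need not mean equal external work. The Background supports more breathing effort with nasal resistance, but it also reports better ventilatory efficiency with this device in healthy subjects. Neither the direction nor the size of a work-rate difference can be derived, and heart-rate steering would limit it.

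**7. Effect on the analysis.** Device size reached and work rate achieved arise after randomisation and may be consequences of the device. Adding them to the model as covariates would not repair the comparison; it would replace the effect of assignment with a conditional contrast that randomisation does not protect. Leaving load out of the model is the right choice for the effect of the programme with the device against the programme without it.

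**The case for a change.** The best case for a change is that every escape from the worst case rests on something unwritten. If heart rate governed, step-up depended on a staff choice. If 6-7 was an end point, step-up would stop once a Borg-steered patient reached it. If the rating followed recovery, it may reflect recovery more than tolerance of the device under load. Each reading can deliver a different inspiratory load from the same text, and another centre could not tell which was used. No recording of speed, watts or minutes is described, so a load difference could not be told apart from a direct device effect.

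Much of this stands as a comment on reporting. The scale, the meaning of the post-session score, the governing criterion and the coordination of the two rules are not written down, and how they fit together is for the investigators to state. It does not show that a stated rule gives a wrong result. A rule that raises resistance when sessions feel easy, and leaves it alone when they are already hard, is ordinary titration; that only patients below target step up is the rule working. Training both arms to equal relative effort is also a legitimate comparison, since the Design section does not promise matched work rates.

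Timing limits the gain as well. The document is written in the past tense and already reports model convergence, so a session log could not be created now. At most, existing records of device size and training load could be described by arm.

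**Conclusion.** The concern does not hold as a defect in the plan. The two Borg ranges are disjoint, by more than 2 points, but they are not shown to apply to the same score at the same moment. The 0-of-24 result depends on three premises that the text does not state and partly contradicts. Any FB-ONB load difference is possible but has no derivable direction or size, and the effect on PImax cannot be computed from the documents.

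What is left is a gap in description that staff running the sessions, and analysts describing them, can fill sensibly. Filling it would alter neither the randomised groups, nor the outcomes, nor the model. This conclusion assumes that the comparison of interest is the programme with the device, as delivered, against the programme without it. A reader who wanted the device effect at a fixed external work rate would be asking a different question, which this design does not claim to answer.
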